## SYNOPSIS

Study Title	The cerebral signature for pain perception and its modulation
Study Design	Prospective study
Intervention Group	All chronic neuropathic pain patients treated with deep brain Stimulation, Spinal Cord Stimulation including targeted stimulation of the Dorsal Root Ganglion, and noninvasive neurostimulation.
Number in Intervention Group	Approximately 50 patients minimum
Control Group	Healthy volunteers with no history of chronic pain, no acute pain, no previous neurosurgery and , no neurological/psychiatric comorbidities.
Number in Control Group	Approximately 50 minimum
Planned Study Period	September 2013 to December 2019
Primary Objective	To determine whether there is cerebral pain signature
Secondary Objectives	To understand how the cerebral pain matrix, including brainstem, anterior cingulate cortex, thalamus and cerebral cortex interact with one another and with the spinal cord and dorsal root ganglia for pain perception and its modulation. Also, to determine whether stimulation has an effect on the autonomic nervous system.
Primary Endpoint	Differences of LFPs of various cerebral nuclei induced by endogenous pain modulation and DBS in chronic pain compared to healthy controls

Secondary Endpoints	Differences of LFPs of various cerebral nuclei induced by Analgesics, Difference in Muscle Sympathetic Nerve Activity (MSNA), Magnetoencephalographic (MEG) or Electroencephalographic (EEG) signals on and off stimulation and other autonomic parameters
Intervention (s)	Quantitative Sensory Testing, and patients' everyday analgesics, Micro-neurography, EMG, and LFP, EEG or MEG recording of brain or DRG, Non-invasive brain stimulation (TMS/tDCS) in chronic pain compared to healthy controls

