## STUDY DESIGN

This is a prospective study. Participants are chronic pain patients admitted to the John Radcliffe Hospital to receive deep brain stimulation, spinal cord stimulation, DRG stimulation, or noninvasive stimulation treatment for pain relief. Their standard clinical treatment involves two operations: stage 1 operation for deep brain or spinal electrode implantation, and stage 2 for pulse generator implantation, which is usually performed one week after stage one operation (for DBS/SCS/DRG patients). The baseline Quantitative Sensory Testing (QST), EEG, MEG, EMG, and Microneurography will take place pre-operatively, within 6 weeks post-operatively and at 6 months. LFP recording will take place between stage 1 and 2 (where appropriate). None of the tests will interfere with the patient's usual treatment.

In addition, a control cohort of healthy subjects that have not experienced chronic pain will be recruited as a comparator group to observe the cerebral signature during non-painful states.

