## Summary of Study Design

Pre-operatively, before 6 weeks post-operatively and at 6 months post-operatively, patients will undergo standard Quantitative Sensory Testing (QST), EEG, MEG, EMG, microneurography and measurement of autonomic parameters (heart rate, 24 hour ambulatory blood pressure, ECG and galvanic skin response). These sessions will not last longer than 2 hours each.

Patients with externalized electrodes are expected to spend one hour a day for 2 days during their stay in the hospital or will be tested intraoperatively. We use computer-based mental tasks to distract patients from their pain, decreasing their pain perception. We record their brain, spinal or DRG electrophysiological signals - local field potentials - to analyse what happens to their nervous system when pain decreases. We will also use electrical, thermal and pressure/ pin prick stimulation on patients' limbs, producing graded painful feeling, and record and analyse their signals during the time to see what kind of signals are related to pain.

A control cohort of healthy age-matched subjects that have not experienced chronic pain will be recruited as a comparator group to observe the normal cerebral signature during unaffected by chronic pain.

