##### Exclusion Criteria

Participants may not enter the study if any of the following applies:

Participants who do not wish to be in the study.

Participants with extreme language barrier that cannot understand the purpose of the study despite the use of an interpreter.

Participants with a history of neurological disorders.

Participants with a history of psychiatric disorders.

Participants who have chronic pain.

Participants who have acute pain.

Participants who had ever undergone neurosurgery.

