#### Procedure:

#### Intervention Group:

Pre-operatively and post-operatively (<6 weeks and 6 months), participants will undergo a full Quantitative Sensory Testing (QST) protocol and Autonomic protocol including microneurography. Participants will also undergo EEG/MEG recording and pre-operative MRI at the Oxford Centre for Human Brain Activity (OHBA) if this has not been done prior to recruitment.

During their inpatient stay, participants will perform a distraction mental task four times. Each time they will be in an 'assigned' state, such as 'resting', with therapeutic stimulation (DBS, SCS, DRG, or noninvasive stimulation), with 'medication' or with 'painful stimulation'. Local field potentials are recorded from the electrodes whilst doing the mental task. Cortical activity will also be recorded using EEG. The order of the patients' states will be randomised. Any experiments in the off medication state will be after 24 hours off analgesics such as paracetamol and codeine-based drugs, making sure that the drug effect has vanished.

Participants will also perform a short computer-based task to measure cognitive performance, including attention, working memory and task-switching. Each subtask is less than 5 minutes, and participants will perform no more than 6 such tasks in succession.

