## INTERVENTIONS

Pre-operatively and Post-operatively we will perform microneurography, QST, tilt table tests, ECG, ambulatory blood pressure, and GSR.

During the distraction and MEG/LFP experiments we will measure patients' ECG, blood pressure and respiratory rate. We will also record their LFPs, MEG, EEG and visual analog scale of pain. In order to know the neural signature for pain, we will use painful stimulation to induce patients' pain perception. This stimulation will take the form of Contact Heat-Evoked Potential Stimulation, electrical stimulation, or mechanical stimulation, with selective stimulation of A-Delta & C-fibers.

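### The Synopsis primary endpoint compares LFPs of cerebral nuclei with healthy controls, who have no implanted brain electrodes; the feasible patient-control EEG/MEG comparison has no labelled endpoint

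*Combined protocol and SAP*

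**What the plan says.** The Primary Endpoint row of the Synopsis reads "Differences of LFPs of various cerebral nuclei induced by endogenous pain modulation and DBS in chronic pain compared to healthy controls". The Secondary Endpoints row begins "Differences of LFPs of various cerebral nuclei induced by Analgesics, Difference in Muscle Sympathetic Nerve Activity (MSNA" and goes on to MEG or EEG signals with stimulation on and off, and to other autonomic measures. It names no control comparator.

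On how LFPs are obtained:
- Study Design: "LFP recording will take place between stage 1 and 2 (where appropriate", that is, between electrode implantation and pulse generator implantation.
- Summary of Study Design: "Patients with externalized electrodes are expected to spend one hour a day for 2 days during their stay in the hospital", or testing is done during surgery.
- Procedure, Intervention Group: "Local field potentials are recorded from the electrodes whilst doing the mental task".
- Interventions, speaking of patients: "We will also record their LFPs, MEG, EEG and visual analog scale of pain".

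On controls, one exclusion criterion is "Participants who had ever undergone neurosurgery", and the Control Group row of the Synopsis says the same. The Control Group procedures are QST, autonomic tests with microneurography, MRI, EEG/MEG, TMS/tDCS and a cognitive battery.

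Background and Rationale says that controls are recruited to validate signatures identified by MEG. Primary and Secondary Endpoints/Outcome Measures assigns LFP changes to the intervention group and MEG/EEG to the comparison with healthy brains. Analysis of Outcome Measures lists QST and EEG/MEG for both groups.

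**The concern.** A primary endpoint has to be a quantity that the planned data can yield. This one needs LFPs from deep brain structures in people who, by the eligibility rules, cannot have electrodes there. An analyst who follows the Synopsis literally has data on one side of the comparison only.

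The comparison for which controls are recruited is feasible but has no rank. If the mismatch is left until analysis, someone must then decide whether the primary result is a within-patient LFP change or a patient-control EEG/MEG difference. A choice made at that stage is no longer pre-specified.

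**Working it through.** **1. Is there a stated calculation to reproduce?** No. The Synopsis gives about 50 patients and about 50 controls, both as minimums. Number of Participants gives about 50 and bases it on the annual number of operations. No alpha, power, effect size or standard deviation is stated.

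**2. Control observations for the primary endpoint.**
- Controls planned: about 50 (Synopsis).
- Implanted brain electrodes per control: 0 (Controls, Exclusion Criteria). Controls do have microneurography needles in the leg and EEG, but neither measures the LFP of a cerebral nucleus.
- Control LFP observations: 50 × 0 = 0, and n × 0 = 0 for any n.
- The standard error of a two-group difference is SD × √(1/n_patients + 1/n_controls). With n_controls = 0 it is undefined, so a larger control group does not help.

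**3. The two inducers in the endpoint.** Endogenous modulation is produced by the distraction task, which is scheduled for the intervention group. DBS is a patient treatment. Neither is among the Control Group procedures. The control side therefore lacks the signal and both of the conditions meant to change it.

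**4. Does another section supply a ranked substitute?**

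| Place | What it offers | Ranked endpoint for patients v controls? |
|---|---|---|
| Synopsis, Secondary Endpoints | MEG/EEG on v off stimulation | No; no control comparator |
| Synopsis, Intervention(s) | Lists EEG/MEG and refers to healthy controls | No; defines no endpoint |
| Primary and Secondary Endpoints/Outcome Measures | LFPs in patients; MEG/EEG for the control comparison | No rank given |
| Analysis of Outcome Measures | QST and EEG/MEG in both groups | No rank given |
| Analysis of Endpoints | Power differences at unspecified frequencies | No contrast named |
| Non-invasive Brain Stimulation | VAS as primary for that sub-experiment | No; a different question |

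**5. What remains computable.** Within-patient LFP contrasts, such as easy or difficult sections against rest sections in State 1, are set out under the questions that each state could address. They need no controls.

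**6. What the EEG/MEG comparison could detect (illustration only).** Assume two-sided alpha 0.05, equal groups, one EEG/MEG measure and no multiplicity adjustment. Detectable standardised difference = (z for alpha + z for power) × √(2/n per group).
- 50 v 50: (1.960 + 0.842) × √(2/50) = 0.56 SD at 80% power; (1.960 + 1.282) × √(2/50) = 0.65 SD at 90%.
- 25 v 25, if the 50 in Number of Participants is the total: 0.79 SD at 80% and 0.92 SD at 90%.

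The EEG/MEG contrast thus has a finite precision at the planned sizes; the LFP contrast with controls has none.

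**The case against.** The strongest reply is that this is a loose phrase in a synopsis. The endpoint section of the body already separates the two data streams in a way that can be carried out, and the analysis section lists for both groups only measures that both groups have. Most of that stands: the defect is an inconsistency between the Synopsis and the body. It does not remove the point, because only the Synopsis ranks the study's endpoints and the body names no replacement.

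It may also be said that the Synopsis does mention EEG/MEG alongside healthy controls, in its Intervention(s) row. That is so, and the comparison is not absent from the Synopsis. But the row lists procedures and sets no endpoint.

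The healthy-volunteer flowchart in Appendix B is not shown in the text available. It could add detail on control visits, but the neurosurgery exclusion is enough to rule out implanted brain electrodes.

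A reader might infer that the study can produce no primary result, or that the controls serve no purpose. The documents do not support either. Within-patient LFP changes survive once the comparator is removed, and controls have a stated role in the EEG/MEG comparison.

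**Conclusion.** The point holds and must be fixed. As written, the primary comparison has 0 control observations out of about 50, and 0 at any control sample size. This rests only on the eligibility criteria and the listed procedures; no statistical assumption is needed. The figures in SD units are illustrative and do not bear on the conclusion.

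The defect is confined to the comparator and to the missing rank of the patient-control EEG/MEG comparison. It does not invalidate the within-patient LFP work.

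A reader might also infer that the EEG/MEG contrast is ready to run in both groups at the pre-operative visit. That is not established. The Magnetoencephalography section describes QST alongside MEG for on and off periods of DRG stimulation, not for a pre-operative recording. Participant recruitment draws on patients whose electrodes are already in place, so some may have no pre-operative study session.

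**What to change.** 1. In the Synopsis, delete the reference to healthy controls from the LFP endpoint. State it as the within-patient change in LFP power at the DBS target, and name as primary one contrast already planned, for example difficult or easy sections against rest sections within State 1.
2. Add patients versus controls as a separate EEG/MEG endpoint with a stated rank. Specify a condition that is run in both groups during the recording, and the patient session used, allowing for patients with no pre-operative session. If the sponsor wants the control comparison as primary, it must be this EEG/MEG contrast and not LFPs.
3. Use the same definitions in the Synopsis, Primary and Secondary Endpoints/Outcome Measures, Analysis of Outcome Measures and Analysis of Endpoints.

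Cost: mainly rewording, with no extra participants and no new LFP recordings. The LFP endpoint gives up its claim to a healthy-control comparison. The change may need approval as a substantial amendment (Approvals). The sponsor must also confirm that the chosen EEG/MEG condition is run in patients; if it is not, it would have to be added to a patient session, and those sessions carry a limit: "These sessions will not last longer than 2 hours each".

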**ABBREVIATIONS**

ACC	Anterior Cingulate Cortex
DBS	Deep Brain Stimulation
DRG	Dorsal Root Ganglion
EEG	Electroencephalogram
EMG	Electromyography
GCP	Good Clinical Practice
IPG	Internal Pulse Generator
ICF	Informed Consent Form
LFPs	Local Field Potentials
MEG	Magnetoencephalography
MRI	Magnetic Resonance Imaging
MSNA	Muscle Sympathetic Nerve Activity
PAG	Periaqueductal Grey
PIL	Participant/ Patient Information Leaflet
QST	Quantitative Sensory Testing
R&D	NHS Trust R&D Department

REC	Research Ethics Committee
SCS	Spinal Cord Stimulation
SOP	Standard Operating Procedure
tDCS	Transcranial Direct Current Stimulation
TMS	Transcranial Magnetic Stimulation
VPL	Ventral Posterolateral thalamic nucleus
VPM	Ventral Posteromedial thalamic nucleus

## BACKGROUND AND RATIONALE

We want to know whether there is a brain signature of pain. Pain perception is very subjective, but if we can find a pain signature, we can detect the objective pain feeling of patients, and we can modulate it to relieve patients' chronic pain.

Besides this, we also want to study the endogenous pain modulation pathway. The more we understand it, the more effective pain treatment we can provide. Pain perception can be altered, and abundant evidence has demonstrated that stimulation of the brainstem (ventrolateral column of the PAG) can activate the endogenous pain modulation pathway to inhibit the pain signal input at the level of the spinal cord. Richardson and Akil, and Hosobuchi and colleagues translated this body of knowledge to clinical use and reported pain relief in patients given chronic stimulation of the PAG. Since then, deep brain stimulation (DBS) of the PAG has been successfully carried out all over the world and has been proved as an effective treatment for pain relief in chronic medicine-refractory pain patients.

Even though the aforementioned mechanism is well-studied, it is still unclear whether the PAG may exert its pain-modulation effect by alternative pathways in addition. Animal studies have shown that the PAG has direct projections to the thalamus in many species. Likewise imaging studies in humans have demonstrated direct connections between the PAG and the thalamus. Therefore, it is reasonable to suggest that the PAG may affect the thalamus to modulate pain perception, and the thalamus, traditionally regarded as a sensory relay centre, may also be able to project to the PAG to modulate pain. However, much less attention has been paid to this suggestion.

In this human study, we take advantage of the DBS of various cerebral nuclei related to pain perception, and use a mental task to induce patients' endogenous pain modulation, to determine whether there is cerebral signature of pain, and to test our two hypotheses: 1. that the PAG modulates pain perception not only via its pathway to the spinal cord, but also via more direct ascending connections to the thalamus; 2. that the thalamus can also affect the PAG to modulate pain, rather than being merely a relay centre.

In addition to these questions, we would also like to investigate the effects of stimulation on the autonomic nervous system to see whether modulation of this system is responsible (at least in part) for the effects of stimulation on pain relief. We have previously shown that stimulation can alter sympathetic nerve activity but would like to investigate this further, especially looking at the peripheral part of the system (dorsal root ganglion (DRG)).

Previous unpublished data suggests that the left side of the brain may modulate pain differently than the right side. In order to ascertain these differences we would utilize the high temporal and spatial resolution of MEG to compare brain signals in various patient states.

In order to validate the clinical significance of MEG-identified signatures, we intend to recruit healthy controls for comparison of neural signatures in pain-free individuals. Furthermore, we wish to evaluate this objectively identified pain signature by localizing the brain structures involved from MRI scans and conducting non-invasive targeted inhibition of these signal with TMS/tDCS to evaluate its impact on pain relief and cognitive function.

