## Primary and Secondary Endpoints/Outcome Measures

In the intervention group, we will observe the changes of LFPs of various cerebral, spinal and DRG nuclei induced by endogenous pain modulation, therapeutic DBS and TMS/tDCS. We will also investigate the differences of LFPs of various nuclei induced by medications.

Cortical signatures of pain will be recorded to identify global changes in neural excitation under chronic pain and therapeutic states. This will be identified using MRI, MEG/EEG recordings and Quantitative sensory testing (QST). In the intervention group, this will be undertaken during endogenous pain modulation, therapeutic DBS, SCS, DRGS and TMS/tDCS. We will also observe changes in autonomic parameters induced by stimulation.

In the control group, we will identify the brain wave patterns via MEG/EEG during quantitative sensory testing (QST), TMS/tDCS and during cognitive tasks in order to compare the chronic pain cerebral patterns with that of the healthy brain.

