## Magnetoencephalography

This procedure is a non-invasive method of detecting changes in the magnetic fields around the scalp which correspond to underlying neural activity. The protocol would involve recording these signals from both hemispheres of the brain, during “on” and “off” stimulation periods to determine if there is a difference in laterality of brain processing during dorsal root ganglion stimulation. We will simultaneously evaluate the aforementioned vital sign evaluations (ECG, blood pressure) and QST to determine the differences between stimulation-induced brain signals and sensory signals and how they correlate with autonomic nervous system function. For those patients who have not undergone MRI Brain pre-operatively, this will be facilitated at the time of MEG recruitment for purposes of pain signal localization.

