### Analysis of Outcome Measures

Outcome measures of both intervention group and control group (QST, EEG/MEG) will be analysed using statistical analysis software and MATLAB. All participant data will be utilized in analysis unless they have withdrawn consent.

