### Analysis of Endpoints

The endpoint analysis will be performed using statistical analysis software and mathematical computational modeling licensed by the University of Oxford. The analysis involves complex signals analysis techniques where significant difference in power at certain frequencies can be determined using custom-made software (based on MATLAB®).

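### The patient-control MEG/EEG comparison is called validation, but nothing fixes the signature beforehand or separates choosing it from testing it

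*Combined protocol and SAP*

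**What the plan says.** The Background and Rationale gives the healthy controls a specific purpose: "In order to validate the clinical significance of MEG-identified signatures, we intend to recruit healthy controls for comparison of neural signatures in pain-free individuals". It also states the ambition behind the signature: "if we can find a pain signature, we can detect the objective pain feeling of patients".

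The signature itself is to be discovered. Under Primary and Secondary Endpoints/Outcome Measures, "Cortical signatures of pain will be recorded to identify global changes in neural excitation under chronic pain and therapeutic states". Controls are recorded during sensory testing, TMS/tDCS and cognitive tasks "to compare the chronic pain cerebral patterns with that of the healthy brain". The Magnetoencephalography section adds "recording these signals from both hemispheres of the brain", with stimulation on and off.

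The analysis text is short. Analysis of Outcome Measures says "All participant data will be utilized in analysis unless they have withdrawn consent". Analysis of Endpoints says that "significant difference in power at certain frequencies can be determined using custom-made software". Neither section, nor any other, names a frequency band, region, direction or primary MEG/EEG contrast. None gives a significance level, a multiplicity method, a held-out set, cross-validation or a second cohort.

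The Non-invasive Brain Stimulation section describes a further check: stimulation aimed at the MEG signal is compared with motor-cortex stimulation and with sham, on VAS, NPSI and EQ-5D.

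**The concern.** A validation step should be able to contradict the finding it validates. That requires the finding to be settled before the test, or the test to use people who did not help to settle it. Here the feature is whichever frequency and region stand out, and the plan does not say that the comparison with controls uses anything other than the patients in whom it stood out.

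Two things follow when a feature is chosen for being extreme and then tested in overlapping data. The false-positive rate rises above its nominal level. The estimated difference is also biased upwards, because it is the largest of many noisy estimates. The primary objective is whether a cerebral pain signature exists, so both bear on the main conclusion. The same signal also sets the target in one of the non-invasive stimulation groups, so a chance selection would weaken that comparison too.

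**Working it through.** **Inputs from the documents.** The Synopsis gives approximately 50 as the minimum in each group. The Number of Participants section gives approximately 50 and bases it on annual operation volume. It states no effect size, SD, power or alpha, so there is no planned figure to reproduce.

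**Assumptions.** Two-sided 5% per test; 20 or 50 candidate frequency-by-region features; correlation between features of 0, 0.5 or 0.8; normal data; no true difference anywhere.

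**Route A: feature chosen from the patient-control contrast and tested in the same people.** With independent features the chance of at least one false finding is 1 − (1 − 0.05)^m:

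- m = 20: 1 − 0.95^20 = 64.2%
- m = 50: 1 − 0.95^50 = 92.3%

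Simulated 50 v 50, taking the feature with the largest absolute t statistic:

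| Candidate features | Correlation 0 | Correlation 0.5 | Correlation 0.8 |
|---|---|---|---|
| 20 | about 64% | 41–44% | 22–23% |
| 50 | about 92% | 62–64% | 29–30% |

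With independent features the selected null feature shows a mean apparent difference of 0.43 SD (20 features) or 0.49 SD (50). At correlation 0.5 these are 0.39 and 0.43 SD. At correlation 0.8 they are a little over 0.3 SD. For scale, the smallest observed difference that reaches p < 0.05 with 50 per group is 1.984 × √(2/50) = 1.984 × 0.2 = 0.40 SD.

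**Route B: feature chosen from the patients' on/off contrast, then the patients' off data compared with new controls.** Only the patients' noise is used twice. The result is counted as confirmation if p < 0.05 in the same direction as the on/off difference, so the nominal null rate is 2.5%. With a within-person on/off correlation of 0.5 to 0.8, the simulated rate is about 5% to 14%. If on and off recordings were uncorrelated it would be roughly 10% to 20%. These rates count every run, whether or not the on/off contrast was itself significant.

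**What adjustment would do.** In route A a max-statistic threshold brings the false-positive rate to 4% to 6%, and Bonferroni to about 5% or below. Neither changes the point estimate at the selected feature, so the apparent 0.3 to 0.5 SD remains.

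**The case against.** There is a good case on the other side, and parts of it stand.

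- **The analysis-set sentence.** A reader might infer from "All participant data will be utilized in analysis unless they have withdrawn consent" that discovery and validation are one analysis by design. The sentence does not say so. It is an inclusion rule, and a cross-validated analysis would also comply with it. The defect is that nothing separates the two steps, not that the plan orders them to be merged.
- **Same participants.** A reader might infer that the signature is validated in exactly the people who produced it, and so can hardly fail. The Background can equally be read as identification in patients followed by comparison with newly recruited controls. That is route B, where the step fails to confirm a null feature about 86% to 95% of the time (100% minus 14% and 5%). If the on/off finding must also be significant at 5%, the joint false rate is 1.4% to 11.9%. With Bonferroni at that stage it is 1% or less.
- **Ordinary multiplicity.** Much of the route A figure is uncorrected multiple testing, and an adjusted threshold would cure the p-value. It would not cure the effect size.
- **Detection of pain.** The statement about detecting pain is a conditional aspiration in the Background. The plan promises no classifier or individual-level accuracy measure, so no bias in such a measure is claimed here.
- **Other checks.** The sham-controlled targeted stimulation comparison brings new outcome data, and a chance signature could fail it. Within-patient modulation by distraction, painful stimulus or analgesia also helps. But the stimulation comparison is framed for SCS/DRG patients, has no stated size or analysis, and asks about pain relief rather than whether the signature separates patients from controls. No section makes the modulation experiments a test of a signature already fixed.

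**Conclusion.** The concern holds in a limited form. The plan labels the patient-control comparison as validation while leaving the frequencies and regions open, and it has no pre-specification, multiplicity control or separation of selection from testing. Followed as written, it permits a selected chance feature to be reported as validated.

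How serious this is depends on a choice that the documents leave open. Choosing from the patient-control contrast gives 22% to 64% false significance with 20 features and 29% to 92% with 50, plus an apparent null difference of about 0.3 to 0.5 SD. Choosing from the on/off contrast gives about 5% to 14% against 2.5%, which is milder but still two to nearly six times nominal (5/2.5 = 2; 14/2.5 = 5.6). All these figures rest on the assumed number of features, correlations and 5% level, and on the Synopsis minimum of 50 per group. The documents do not support saying that the validation cannot fail, or that the larger figures apply whichever way the feature is chosen.

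**What to change.** In Analysis of Outcome Measures and Analysis of Endpoints, adopt one of two routes.

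1. Fix the frequency band, region, direction and primary contrast in writing before the patient-control data are analysed.
2. Choose them inside cross-validation folds formed by participant. Report the patient-control difference and the correlation with VAS only from left-out participants, with a permutation p-value that repeats the selection step in every permutation.

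Under either route, label any in-sample difference at a selected frequency exploratory, and use the word validated only for the pre-specified or out-of-sample result.

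The cost is some analysis code, a few sentences, and probably a less favourable reported effect. No patients or recordings are added, and all participants still contribute. Cross-validation is preferable to a single half-split here. For an assumed true difference of 0.5 SD, one pre-specified feature has 70.5% power with 50 v 50, but a held-out test in 25 v 25 has 42.4%.
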